#### **8.3.6.1.1. Immunology Exploratory (PBMC and binding IgG vs IgM antibody response)**

The exploratory immunology samples (peripheral blood mononuclear cells [PBMC] and serum for IgG and IgM antibody response) are being collected to characterize the cell and humoral immune response to the vector capsid protein.

These samples will be destroyed upon or before completion of the last clinical study report for the study.

#### **8.3.6.2. Analysis of FIX Inhibitor**

During all study periods, blood samples will be collected for measurement of FIX inhibitor as specified in the [SoA](#) section of the protocol.

- Samples collected will be analyzed using a validated analytical method in compliance with standard operating procedures (SOPs). The samples must be processed and shipped as indicated in the instructions provided to the investigator site to maintain sample integrity. Any deviations from the sample handling procedure (eg, sample collection and processing steps, interim storage, or shipping conditions), including any actions taken, must be documented and reported to the sponsor. On a case by case basis, the central laboratory may make a determination as to whether sample integrity has been compromised. Any deviation from the specified sample handling procedure resulting in compromised sample integrity will be considered a protocol deviation. These data will not be included in the clinical study report (CSR).

#### **8.3.6.3. Analysis of Cellular Immune Response by ELISPOT (enzyme-linked immunospot)**

This is a quantitative method for measuring relevant parameters of T cell activation. The sensitivity of ELISPOT allows the detection of low-frequency antigen-specific T cells that secrete cytokines and effector molecules. Specimen for PBMC by ELISPOT will be collected at times specified in the [SoA](#).

Specimen is to be collected prior to initiating the corticosteroid treatment. If not collected prior to initiation, it must be collected within 24 hours of administering corticosteroids. It is highly recommended that participants who are initiated on corticosteroid treatment be treated with a gastric acid reducer, preferably a proton pump inhibitor (PPI) (eg, omeprazole), or alternatively a histamine type 2 (H2) antagonist (eg, ranitidine) for the duration of the corticosteroid course.

Whole blood specimens (approximately 48 mL) will be collected in sodium heparin vacutainer tubes to provide PBMC to monitor T cell responses to AAV capsid and transgene products at times specified in the [SoA](#) of the protocol.

Detailed collection, processing, storage, and shipment instructions are provided in the central laboratory manual.

As part of understanding of the immunogenicity of the study drug, samples may be used for further characterization and/or evaluation of the bioanalytical method. These data will be used for internal exploratory purposes and will not be included in the clinical report. Samples collected for this purpose will be retained in accordance to local regulations and if not used within this timeframe, will be destroyed.

### **8.3.7. Disease-Related Events and/or Disease-Related Outcomes Not Qualifying as AEs or SAEs**

The disease related events (DREs) for this study include episodes of bleeding related to hemophilia B. The bleeding episode itself is not reported as an AE, unless the bleeding episode meets the criteria outlined below.

Consideration on whether the bleeding event is a DRE is based on investigator determination and bleeding events recorded by the participant in their electronic diary will be reviewed by the investigator and assessed against reporting obligations for S/AE.

Bleeding, not due to the participant's hemophilia, will be recorded as an AE, and not a DRE. If any of the following conditions apply, then the event must be recorded and reported as an AE or SAE (instead of a DRE):

- Bleeding events that require hospitalization or meet other SAE criteria (see [Appendix 3](#)) should be reported as SAEs. When bleeding episodes that meet the SAE criteria are recorded on the AE CRF, the location (site) of the bleed and the etiologic classification as spontaneous or traumatic should be included (as described in [Section 8.1.1](#) and [Appendix 2](#)).
- The bleeding event is, in the investigator's opinion, of greater intensity, frequency, or duration than expected for the individual participant.

OR

- The investigator considers that there is a reasonable possibility that the bleeding event was related to study intervention.

### **8.3.8. Immunomodulation Optimization (Presumed T-Cell Activation)**

A tapering course of oral corticosteroids (ie, prednisone/prednisolone) will be the first consideration for suppression of apparent immune hepatitis. The rationale for this approach is that corticosteroids are effective in severe autoimmune hepatitis, a disease in which hepatocytes are attacked by epitope-specific cytotoxic T-Lymphocyte. The mechanism for

this immune reactivity is not clear, but viruses may be causal. It is also possible that an elevation in liver transaminases is not due to immune responses.

While not all elevations in liver transaminases may be immunologically mediated, the decision to treat will not be delayed while attempting to decipher the etiology. It is highly recommended that participants who are initiated on corticosteroid treatment be treated with a gastric acid reducer, preferably a proton pump inhibitor (PPI) (eg, omeprazole), or alternatively a histamine type 2 (H2) antagonist (eg, ranitidine) for the duration of the corticosteroid course. Due to the importance of timely intervention of corticosteroids, decisions to begin treatment will be based on local laboratory values. Based on guidelines published by the American Association for the Study of Liver Diseases and in the absence of alternative etiology, and from the study data of the SJ-UCL group along with the Phase 1/2a study, treatment with corticosteroids for vector-induced hepatitis would be highly recommended if any of the criteria are met:

- Transaminase increase, per local lab results:
  - Single increase  $\geq 1.5$  fold of the lowest transaminase value, since screening into the study and prior to infusion.
    - For example, a participant may have an ALT of 35 U/L prior to infusion, but at week 5 the value increases to 53 U/L. This increase would be enough to initiate treatment even though the values are within normal range.
  - Consecutive increases (an increase in transaminases on two subsequent blood tests independent of FIX:C values). Following the trend is especially important as it is possible that LFTs seen post-infusion may be below that seen during screening/baseline. In these situations, following for consecutive increases/trends is particularly important.
    - For example, a participant may have an ALT of 18 U/L. Then on the next two lab draws (obtained during a study visit or unplanned visit) the values increase to 22 U/L and then 26 U/L, this increase would be enough to initiate treatment even though the values are within normal range.
    - For example, a participant may have an ALT of 38 U/L as the baseline value. Post-infusion, the ALT values are lower than that seen during screening and range from 18-22 U/L over the first few weeks. Then on the next 2 laboratory draws (obtained during a study visit or unplanned visit), the values increase to 29 U/L and then 37 U/L. This increase would be enough to initiate treatment even though the values are both below baseline and within normal range.
  - **Note:** Any delay or deviation in the initiation of corticosteroid treatment, based on the transaminase increase points above, must be discussed with the sponsor's

medical monitor in the context of the overall clinical management plan to ensure participant safety.

- FIX:C decrease, per local lab results:
  - Single significant decrease, not associated with a recent infusion of external FIX product.
    - For example, a participant may have a FIX:C of 51 IU/mL at Week 4, but at Week 5 the value decreases to 28 IU/mL. This decrease would be enough to initiate treatment.
  - Consecutive decreases (a decline in FIX activity on two consecutive blood tests independent of transaminase values) if occurring during the first 120 days post-infusion.
    - For example, a participant may have a FIX:C value of 34 IU/mL at Week 4. Then on the next two lab draws (obtained during a study visit or unplanned visit) the values decrease to 27 IU/mL and then 24 IU/mL, this decrease would be enough to initiate treatment.

If occurring beyond 120 days post-infusion, the investigator should contact the sponsor’s medical monitor to discuss prior to initiating corticosteroids unless otherwise clinically indicated (eg, a decline in FIX:C level thought to be beyond the margin of error for FIX:C assay or biological fluctuation).

- **Note:** Any delay or deviation in the initiation of corticosteroid treatment, based on the FIX:C decrease points above, must be discussed with the sponsor’s medical monitor in the context of the overall clinical management plan to ensure participant safety.

**Table 1. Recommended Regimen for Oral Corticosteroids**

Schedule (oral corticosteroid treatment regimen)	Prednisolone/Prednisone (mg/day)
Week 1	~60 – 100*
Week 2	60**
Week 3	40
Week 4	30
Week 5	30
Week 6	20***
Week 7	15
Week 8	10

\* Mainly based on body weight.

\*\* See the paragraph below this table.

\*\*\* Maintain at 20 mg/day until transaminases return to baseline, then reduce by 5 mg/day until 10 mg/day are achieved then reduce by 2.5 mg/week up to 5 mg daily. If available, ELISPOT results will be monitored during tapering.

Approximately 60-100 mg/PO (orally) qd (once a day) of oral corticosteroids for the first week is recommended as the starting dose unless the investigator believes a different regimen should be implemented based on the participant's medical history. Per the judgment of the investigator, the first week dose can be extended to another week if the participant has no adverse effect. The subsequent prednisolone/prednisone taper should not be started until the ALT and/or AST have declined at least two consecutive lab draws, or have returned to approximately baseline (pre-administration) levels and any decline in FIX:C activity has plateaued. See [Table 1](#) above.

The following schedule of combined oral corticosteroids and intravenous corticosteroids (methylprednisolone) is recommended if there is no evidence of resolution of transaminase elevation while on oral corticosteroids treatment alone.

**Table 2. Recommended Regimen for Combination Intravenous and Oral Corticosteroids**

Schedule (corticosteroid treatment regimen)	Oral Prednisolone/Prednisone (mg/day)	Intravenous Methylprednisolone (g/day)
Days 1 to 3	n/a	1
Days 4 to 7	20	n/a
Week 2	60	n/a
Week 3	60	n/a
Week 4	40	n/a
Week 5	30	n/a
Week 6	30	n/a
Week 7	20	n/a
Week 8	10	n/a
Week 9	5	n/a

The investigator will have flexibility in implementing the immunomodulatory regimen since the exact regimen and course will depend on clinical circumstances. The long-term side effects of the immunomodulatory drugs to be considered in this study are well characterized. Participants who develop immune hepatitis will be monitored closely to minimize the risk of the side effects. To use the lowest effective dose and to shorten the duration of the immunosuppressive therapies, tapering of the regimen will start as soon as there is evidence of resolution of hepatic transaminases elevation and FIX:C activity has plateaued. If available, ELISPOT results will be monitored during tapering. While on immunomodulatory regimens, participants will also be monitored for side effects, such as opportunistic infections. Antibiotics or other medications to minimize the risk of opportunistic infection may be prescribed at the discretion of the investigator. All events related to the use of immunomodulatory drugs (eg, hyperglycemia, weight gain, infections) will be recorded as adverse events connected to their use.

- If 2 or more participants are non-responsive to immunomodulatory regimens, or if the value of the transaminases continues to rise, consideration of more intensive immunomodulatory regimens will be entertained per discussion between the sponsor

medical monitor and the investigator. The sponsor will convey the information to the External Data Monitoring Committee (eDMC).

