Vector Shedding Analysis by PCR (CL)		X	X*	Weekly, as needed# Utilize mobile phlebotomy / home health services, as needed										
 
•# Plasma, PBMC, saliva, semen, and urine specimens will be collected at baseline and every week after IP administration until 3 consecutive specimens test negative for the given specimen type.
 
•Semen samples can be collected at home the night before a clinic or mobile phlebotomy/ home health service visit and stored in the participant’s freezer until the clinic or mobile phlebotomy/ home health service visit, with the exception of semen samples collected as part of the optional vector shedding sub-study (see bullet point below)
 
•*Optional Vector Shedding Sub-study: Additional (2 hrs (±30 minutes), 24 hrs (±3 hrs), 72 hrs (±4 hrs) after completion of IP infusion and IV line flush on Day 1) samples (plasma, PBMC, saliva, semen, and urine) will be collected from some participants (n=12) who consent to participate in an optional sub-study. Utilize mobile phlebotomy/ home health services as needed.
 

Any Additional Safety Tests	Ongoing (as needed)												Additional laboratory testing may be conducted as deemed clinically necessary by the investigator to ensure safety of participants.	
Adverse Events	Ongoing (including unscheduled visits)												During the Short-Term Monitoring Period (up to and including 52 weeks post-infusion) all SAEs and AEs (including medically important events) will be collected ( Appendix 3 ).	

Procedures Year 1	Screening Period	Baseline Period	IP Infusion	Week 1-12 (± 2 days)					Week 13-52 (±1 week)					
 
•The following Screening labs should be collected in the absence of residual infused FIX (FIX trough): FIX activity, hemostasis markers, inhibitor testing.
 
•The Screening and Baseline period may be extended, upon consultation with the sponsor’s medical monitor. Reason must be recorded in the source documents. Depending on the length of extension (of either period), the medical monitor may request to have visit procedures repeated.
 
•After determination of eligibility, FIX replacement therapy and IP Infusion will be planned at a time when a routine FIX infusion will occur during the study visit on Day 1.
 

Study Visit	1	2	3	4*	5	6	7	8	9	10	11	12	13	

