### **8.3.1. Time Period and Frequency for Collecting AE and SAE Information**

All ongoing AEs and SAEs in the lead-in study (C0371004), including events of special interest, as defined in the lead-in study (C0371004), will be collected as medical history for this study. Historical data on Demographics, Medical, Surgical and Hemophilia History will be captured from the lead-in study. Any new AEs/SAEs after completion of the lead-in study will follow the AE reporting process ([Appendix 3](#)).

The time period for actively eliciting and collecting AEs and SAEs (“active collection period”) for each participant begins from the time the participant provides informed consent, which is obtained before the participant’s participation in the study (ie, before undergoing any study-related procedure and/or receiving investigational product), through and including 6 years after the last administration of the investigational product, or at EOS for participants who discontinue. The active collecting period for this study is categorized into Short-Term and Long-Term Monitoring Period as defined later in this section.

For participants who are screen failures, the active collection period ends when screen failure status is determined.

Follow up by the investigator continues throughout and after the active collection period and until the event or its sequelae resolve or stabilize at a level acceptable to the investigator, and Pfizer concurs with that assessment.

If the participant withdraws from the study and also withdraws consent for the collection of future information, the active collection period ends when consent is withdrawn.

If a participant discontinues study intervention because of an AE or SAE, the AE or SAE must be recorded on the CRF and the SAE reported using the CT SAE Report Form.

During the Short-Term Monitoring Period (up to and including 52 weeks post-infusion) all SAEs (including medically important events, see [Appendix 3](#)) and AEs will be collected.

During the Long-Term Monitoring Period (Week 53 post-infusion to EOS) the following AEs will be collected:

- SAEs (including medically important events, [Appendix 3](#)).
- Non-serious AEs determined to be related to IP by the investigator or where causality is unknown.

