#### During the Long-Term Monitoring Period (Week 53 post-infusion to EOS)

Safety Event	Recorded on the CRF	Reported on the CT SAE Report Form to Pfizer Safety Within 24 Hours of Awareness
SAE (including a medically important event – see Section 10.3.2 Definition of SAE, Other Situations)	All	All

Non-serious AE
 
 
determined to be related to the investigational product by the investigator;
 
where causality is unknown.
 
	
All
	
None

Exposure to the investigational product under study during pregnancy, and occupational exposure
	
None
	
All (And EDP supplemental form for EDP)
 
Note: Include all SAEs associated with exposure during pregnancy. Include all AEs/SAEs associated with occupational exposure.

- When an AE/SAE occurs, it is the responsibility of the investigator to review all documentation (eg, hospital progress notes, laboratory reports, and diagnostics reports) related to the event.
- The investigator will then record all relevant AE/SAE information in the CRF.
- It is **not** acceptable for the investigator to send photocopies of the participant's medical records to sponsor in lieu of completion of the sponsor/AE/SAE CRF page.
- There may be instances when copies of medical records for certain cases are requested by Pfizer. In this case, all participant identifiers, with the exception of the participant number, will be redacted on the copies of the medical records before submission to Pfizer.
- The investigator will attempt to establish a diagnosis of the event based on signs, symptoms, and/or other clinical information. Whenever possible, the diagnosis (not the individual signs/symptoms) will be documented as the AE/SAE.

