3.5.1. Adverse Events

The summary tables of AE will be based on data collection presented in Figure 2 below. The time period for actively eliciting and collecting AEs and SAEs ("active collection period") for each participant begins from the time the participant provides informed consent, which is obtained before the participant's participation in the study (i.e., before undergoing any study-related procedure and/or receiving PF-06838435), through and including 6 years after the last administration of the PF-06838435, or at End of Study (EOS) for participants who discontinue. The active collection period for this study is categorized into Short Term (up to and including 52 weeks post PF-06838435 infusion). The Long-Term Monitoring Period is defined as Week 53 post PF-06838435 infusion until EOS.

[figure not shown]
During the Short Term Monitoring Period, all SAEs (including medically important events (MIE), see protocol Appendix 3) and all non-serious AEs will be collected.

[figure not shown]
During the Long-Term Monitoring Period the following adverse events will be collected:

- SAEs (including MIEs, see protocol Appendix 3);
- Non-serious AEs determined to be related to PF-06838435 by the investigator or where causality is unknown;

Adverse Events of Special Interest (AESIs), as detailed in protocol Appendix 3, will be summarized. There is no lag time specified for adverse event reporting in this study.

Treatment emergent adverse events (TEAEs) include any adverse events that occur on or after the infusion of PF-06838435. Missing severity will be not imputed. AEs will be coded using the version of Medical Dictionary for Regulatory Activities (MedDRA) available at the time of database release and summarized by system organ class and preferred term.

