6.6.1. Adverse Events

An overall table summarizing AEs reported during the entire study will be sorted by system organ class and preferred term. Per protocol, adverse events assessed as non-serious and unrelated to study drug are reported within the first year post infusion only and not subject to reporting thereafter. As a consequence, the all-causality TEAE tables will include a footnote to convey non-serious unrelated AE were collected over the initial year and not the subsequent 5-year study duration for a given participant.

All AEs occurring during the first year (up to and including 52 weeks post PF-06838435 infusion) will be summarized, sorted by system organ class and preferred term. All AE summary tables will be generated to display all AEs, relationship to study drug, severity of the AE ('Mild', 'Moderate', and 'Severe'), and if serious AE or not.

All serious AEs, treatment-related non-serious AEs, AESIs, AE leading to study discontinuation, and AE leading to death will be summarized per Pfizer Data Reporting Standard, for AE reported during short term (up to and 52 weeks post PF-06838435 infusion)

and AE reported during the entire course of study including long-term monitoring (post PF-06838435 infusion to Year 6 or EOS), respectively.

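### Protocol 8.3.8 requires every immunomodulator-related event to be recorded as an adverse event, but the collection rules from Week 53 omit the non-serious ones judged unrelated to the IP

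*Protocol*

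**What the plan says.** The broad instruction is in Protocol 8.3.8, in the text below Table 2: "All events related to the use of immunomodulatory drugs (eg, hyperglycemia, weight gain, infections) will be recorded as adverse events connected to their use". It names no time window and no seriousness threshold.

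The general collection rules depend on the period.

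- **To Week 52.** The Year 1 Schedule of Activities (SoA) says: "During the Short-Term Monitoring Period (up to and including 52 weeks post-infusion) all SAEs and AEs (including medically important events) will be collected". There is no conflict in this period.
- **Week 53 to end of study.** All SAEs are collected. For the rest, Protocol 8.3.1 and the Years 2 to 6 SoA collect "Non-serious AEs determined to be related to IP by the investigator or where causality is unknown". The long-term table in Protocol 10.3.3 uses the same test, namely events "determined to be related to the investigational product by the investigator" or of unknown causality. SAP 3.5.1 repeats it: "Non-serious AEs determined to be related to PF-06838435 by the investigator or where causality is unknown". SAP 6.6.1 adds that "adverse events assessed as non-serious and unrelated to study drug are reported within the first year post infusion only", and plans a footnote to the all-causality tables saying so.

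Protocol 8.3.1.2 adds a third reading. Its first sentence asks for every non-serious AE in the active collection period to be recorded, and 8.3.1 runs that period for six years. Its second paragraph then points to 10.3.3.

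Corticosteroid use after Week 52 is foreseen. The Years 2 to 6 SoA has a PBMC sampling row for the case where such treatment is needed for a suspected T-cell response. For consecutive FIX:C decreases, 8.3.8 says "If occurring beyond 120 days post-infusion, the investigator should contact the" sponsor's medical monitor before starting corticosteroids, and sets no upper time limit.

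**The concern.** Protocol 4.2 introduces immunomodulation to limit the hepatic immune response and maintain FIX expression. Its toxicity therefore belongs to the benefit-risk of the gene therapy, and safety over six years is a stated objective in Protocol Section 3. The examples in 8.3.8 (raised glucose, weight gain, infection) are often non-serious. After Week 52 the test for a non-serious AE turns on the IP, and Protocol 6.1 lists only PF-06838435 as the intervention. An event firmly attributed to prednisone, and judged not to be caused by the vector, has a recording instruction in 8.3.8 but no place in the long-term list.

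A site following 8.3.8 would record it; a site following 8.3.1 or 10.3.3 would not. The long-term count of such events would then depend partly on which section each site followed. If some sites do record them, the planned SAP 6.6.1 footnote would also misdescribe the data.

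**Working it through.** The plan states no figure to reproduce. The check is a comparison of text with a little arithmetic.

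**1. Which events fall in the gap after Week 52**

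- Serious, any cause: collected.
- Non-serious, related to the IP: collected.
- Non-serious, causality unknown: collected. Protocol 10.3.3 also treats an unknown relation to the IP as related for reporting.
- Non-serious, attributed to an immunomodulatory drug and judged unrelated to the IP: required by 8.3.8, absent from 8.3.1, the Years 2 to 6 SoA, 10.3.3 and SAP 3.5.1, and treated as first-year-only by SAP 6.6.1.

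Only the last class is in conflict. No section exempts it from the narrower rule.

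**2. Onset**

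An AE that begins by Week 52 is collected, and 8.3.1 and 8.3.3 require follow-up until it resolves or stabilizes. Only new onsets after Week 52 are affected.

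**3. Which courses reach Week 53**

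A course of L weeks starting in Week s ends in Week s + L − 1. It reaches Week 53 when s ≥ 53 − L + 1.

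- Table 1, L = 8: s ≥ 46.
- Table 2, L = 9: s ≥ 45.

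These hold for standard-length courses. The Table 1 footnote and the text below it allow a course to run longer, in which case an earlier start would also reach Week 53.

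**4. Period under the narrower rule**

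Protocol 4.2 gives 52 + 260 = 312 weeks, so the narrower rule covers 260/312 = 83.3% of follow-up time.

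**5. Number of participants**

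The documents give no rate of corticosteroid use after Week 52. For scale only, Protocol 2.2.2 reports 2 of 10 Phase 1/2 participants treated with prednisone. The exact 95% interval runs from the 0.025 quantile of Beta(2, 9), 2.5%, to the 0.975 quantile of Beta(3, 8), 55.6%. Assuming that rate for 40 participants gives 40 × 0.20 = 8 with any corticosteroid use (40 × 0.025 ≈ 1 to 40 × 0.556 ≈ 22). Those with a course after Week 52 would be a subset of unknown size.

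**6. Whether other data fill the gap**

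Weight and glucose are scheduled at Weeks 78, 104, 130, 156, 208, 260 and 312. The shortest interval is 26 weeks, so an 8- or 9-week course can begin and end between visits. Neither measure detects an infection.

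**7. Whether the course itself is recorded**

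After Week 52, Protocol 6.5, the SoA and SAP 3.5.4 record concomitant therapy only when it is associated with a reportable AE. Under 8.3.8 a course may be started for transaminase values still within the normal range, or for a FIX:C decline. Protocol 10.3.1 says lack of efficacy is not in itself an AE. A late course may therefore have no qualifying AE to attach to, yet SAP 6.6.2 summarizes total corticosteroid dose and time. Unless a dedicated form not described in these documents captures them, such courses could be missing from that summary.

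**The case against.** The strongest reply is that limited long-term AE collection is deliberate. It appears consistently in the SoA, 8.3.1, 10.3.3 and the SAP, and 8.3.8 itself calls the long-term side effects of these drugs well characterized. On that view, one sentence in 8.3.8 was simply not bounded in time, and bounding it would resolve the conflict as well as widening collection. That stands, and the fix offers it as an option.

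A reader might infer that the harm of late immunosuppression goes uncounted, or that the six-year tables will show no non-serious steroid toxicity after Week 52. The documents do not support this:

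- A serious infection on corticosteroids is still an SAE and is still collected.
- Attribution to a steroid and to the IP are not stated to be mutually exclusive. An investigator may see a reasonable possibility that an event arising during treatment of vector-induced hepatitis is also related to the IP.
- Section 8.3.8 and the first sentence of 8.3.1.2 may lead some sites to record the remaining events. SAP 6.6.1 plans an overall table of AEs reported during the whole study, where they would appear.
- Glucose and weight are still measured, and SAP 6.6.2 plans shift tables for chemistry.

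Nor does the 83% mean that 83% of steroid toxicity is at risk. It is calendar time. The plan concentrates surveillance early, with two to three samples a week for 12 weeks, and the consecutive-decrease trigger for FIX:C leads directly to treatment only in the first 120 days. Late courses may be few.

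**Conclusion.** The inconsistency is real, lies in current text and is narrow. New-onset, non-serious AEs after Week 52 that are attributed to immunomodulatory drugs and judged unrelated to the IP would be captured inconsistently or lost. The supportable conclusion is uneven capture, not a certain zero. Its size in participants cannot be derived from the documents and may be small. A second gap goes with it: a late corticosteroid course not tied to a reportable AE may be absent from the exposure summaries, which would leave no reliable denominator for whatever steroid-related events are recorded.

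This rests on two assumptions: that some courses are given after Week 52, which the SoA foresees, and that some resulting events are judged unrelated to the IP. It is worth correcting because it determines which six-year safety data are collected, and the correction is cheap.

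**What to change.** Reconcile the passages in one of two ways.

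**Preferred.** Add to the long-term list in Protocol 8.3.1, the Years 2 to 6 SoA, Protocol 10.3.3 and SAP 3.5.1 a further category: non-serious AEs that the investigator attributes to immunomodulatory drugs given for a presumed immune response to the vector. Amend the SAP 6.6.1 footnote to match. In Protocol 6.5, the SoA and SAP 3.5.4, record those drugs after Week 52 whether or not an AE is reported, so that the SAP 6.6.2 summaries are complete. For any participant already past Week 52 when the change takes effect, the tables should state from when these data were collected.

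**If the narrower rule is intended.** Limit the 8.3.8 sentence to the Short-Term Monitoring Period, and state in the safety tables that later non-serious steroid-related events were not collected.

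The preferred change costs wording in the protocol and SAP, plus a few AE and medication entries for participants on these drugs after Week 52. It needs no new visits or tests and changes no dose or clinical rule. The alternative costs wording only.
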